**Abbreviations Used in the Protocol and Study:**

- AI: Associate Investigator
- ANOVA: Analysis of variance
- ANCOVA: Analysis of covariance
- AR: Army Regulation
- ARL: Army Research Laboratory
- AWS: Amazon Web Services
- CAC: Common Access Card
- CMPN: Center for Military Psychiatry and Neurosciences
- CR: Continuing Review
- CSV: Comma Separated Values
- DoD: Department of Defense
- FBI: Federal Bureau of Investigation
- FedRAMP: Federal Risk and Authorization Management Program
- GLM: General Linear Model
- HAB: Hostile Attribution Bias
- HBMT: Hostile Bias Modification Training
- HSPB: Human Subjects Protection Office
- IA: Information Assurance
- ICD: Informed Consent Document
- IRB: Institutional Review Board
- LSD: Least Significant Difference
- MCAR: Missing Completely at Random
- MOMRP: Military Operational Medicine Research Program
- MPB: Military Psychiatry Branch
- MRMC: Medical Research and Materiel Command
- MS: millisecond
- MTF: Medical treatment facilities
- MTurk: Amazon Mechanical Turk
- OPSEC: Operational Security
- ORP: Office of Research Protections
- PI: Principal Investigator
- PII: Personally identifiable information
- RA: Research assistant
- SOP: Standard operating procedure
- SPSS: Statistical Package for the Social Sciences
- SSL: Secure Sockets Layer
- USA: United States of America
- USAMRMC: U.S. Army Medical Research and Materiel Command
- WRAIR: Walter Reed Army Institute of Research

## 2 PRÉCIS

Aggression refers to causing harm to someone who is motivated to avoid that harm (Anderson & Bushman, 2002). One key predictor of aggression is the extent to which the victim believes that the provocateur acted in an intentionally hostile manner (e.g., being shoved on purpose) versus not intending to be hostile (e.g., being shoved by mistake; De Castro, Veerman, Kooops, Bosch, & Monshouwer, 2002). Hostile attributional bias (HAB) refers to the tendency to attribute hostile intentions to the actions of others when contextual cues are ambiguous (Milich & Dodge, 1984). Hostile interpretations of provoking events are automatic and require slow and effortful mental processing to replace (Gilbert & Malone, 1995; Carlston & Skowronski, 1994, 1995; Winter & Uleman, 1984; Wilkowski, Robinson, & Troop-Gordon 2010). Differences between the cognitive accessibility of hostile vs. non-hostile concepts is an important predictor of HAB and aggression (e.g., Bartlett et al., 2009; Meier and Robinson, 2004; Graham and Hudley, 1994). Training programs that emphasize increasing the accessibility of non-hostile concepts in the face of ambiguous information and reinforce inhibiting rapid hostile attributions may reduce HAB (Hawkins and Cogle, 2013). In a previous study (WRAIR #2574), a training task called Hostile Bias Modification Training (HBMT), developed jointly by WRAIR and ARL significantly reduced HAB on a validated measure. The present study would extend these findings to determine if HBMT can reduce actual expressions of low-intensity, normal aggressive behavior (e.g., angry driving) assessed via anonymous surveys.

The study would utilize up to 400 volunteers (200 completers) recruited via an online commercial recruitment platform to participate in an online study. Volunteers will be asked to participate at two time-points. At time-point one, volunteers would be randomly assigned to complete one of two versions of HBMT. One version is designed to train the brain (rehearse and reinforce) to seek positive interpretations of ambiguous social cues and to inhibit thoughts and behaviors related to hostility. The second is a placebo version that is not expected to affect attitudes, cognitions, or behaviors. These versions were validated in a prior study (WRAIR #2574). Volunteers will also complete some brief surveys to assess state emotion, trait anger, and HAB. Volunteers will be asked to return between 24 and 96 hours later to complete another brief measure of HAB, state emotion, and a brief self-report survey about their online (public behavior only), driving, and other behaviors over the preceding 24 hours. We hypothesize that volunteers who receive the genuine training will display the less hostile bias and report lower anger and aggression in their daily behaviors when assessed at the second time-point.

If successful, these findings would provide evidence that HBMT is effective in affecting real-life behaviors and help convince potential stakeholders of the value of HBMT. Future research could validate effectiveness in operational units as well as with unhealthy populations (e.g., anger management groups). Future research could also test the effectiveness of HBMT on behavioral health outcomes for usage by clinicians and portable use by individuals with unhealthy hostile bias and problems with social aggression when isolated from traditional behavioral health care (e.g., far forward deployed units).

### 3 STUDY SUMMARY

#### 3.1 Objectives

Primary objective of the present protocol is:

- a. Evaluate the effect of hostile bias modification training (HBMT) on real-life behaviors (reducing typical public displays of aggression) and emotions (reducing anger).

Secondary objective of the present protocol is:

- b. Identify shifts in HAB as an underlying cognitive mechanism linking HBMT to behavior change.

#### 3.2 Target Population and Number of Volunteers

The target population for this study is adult male and female volunteers. The study requires up to 400 volunteers (200 completers) successfully complete the study to run statistical analyses. We anticipate up to 50% drop-out between study session 1 and 2 as attrition is high in MTurk populations (Mason and Suri, 2012). A “completer” is defined as completing the HBMT with at least 60% of the stems completed correctly and participating at both T1 and T2.

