### 7.2 Determination of Sample Size

200 volunteers (100 completers per condition) are needed to achieve statistical power of 80% and equal groups. The previous (and only other) study to test HBMT found a large effect of the real (vs. placebo) training on HAB ( $d = .78$ ), when HAB was assessed immediately after HBMT. However effect sizes are expected to be smaller in the present study as actual behavior is being assessed and there is a greater time delay (24-96 hours) between HBMT and the behavioral assessment. We will divide this effect size approximately in half ( $d = .4$ ) in our prediction for the second study. Given this effect size, a minimum of 200 completers who follow all task instructions will be needed to achieve 80% power.

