### **9.4 Accounting for Missing, Unused, and Spurious Data**

Missing data will be identified as such in the database and will not be imputed or replaced for analytic purposes. Little's Missing Completely at Random (MCAR) test (Little, 1988) will be used to confirm that all missing data were missing "completely at random". Participants with small amounts of missing data ( $\leq 15\%$ ) will be excluded from analyses pairwise, whereas volunteers with large amounts of missing data ( $>15\%$ ) will be excluded listwise. Outliers are defined as individual scores that fall beyond an acceptable range (1.5 inter-quartile ranges above the third quartile or below the first quartile). Outliers will be identified as such in the database, and will not be included in data analyses, or will be transformed as appropriate for use in the data analytic strategy.

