## 13 APPENDICES

### Appendix A: Recruitment Materials

#### MTurk Advertisement

(Note: the field titles and sections are standardized on MTurk).

**Title:** Psychology Study: Help Scientists Test the Relationship Between a Vocabulary Task and How People Behave in Daily Life.

**Description:** This is a two part research study. At time-point one, you will fill out some brief personality surveys. You will also read several short scenarios and imagine how you would react and/or interpret these situations in real life. You will also complete a vocabulary task where you will sort word fragments based on type as quickly as you can. This will take approximately 30 minutes. You will be asked to return in 24-96 hours for part two where you will repeat a similar scenario reading activity as during time one and fill out a brief questionnaire about your recent behaviors. This second time-point will take about 25 minutes.

**Keywords:** Psychology, Study, Experiment, Science, Sorting, Reading

**Payment:** \$5 (\$3 at time-point one and \$2 at time-point two)

**Number of assignments per HIT:** 400

**Time Allotted Per Assignment:** 1 hour

**HIT Expires in:** [TBD]

**Auto-approve and pay workers in:** 8 hours

**Appendix B: Angry Cognitions Scale  
(ACS)**

**Directions:** Below are several scenarios followed by types of thoughts people often have in similar situations. For each scenario, imagine that what is being described has just happened to you. Then, read each thought and fill in the circle indicating how likely you would be to have that thought or one similar to it in that situation. There are no right or wrong answers and you are not being asked whether these thoughts are appropriate - only how likely you would be to have similar thoughts. Please respond to all of the thoughts for each scenario.

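### At the plan's worst-case 50% drop-out, the 400 cap leaves exactly 200 returners and no margin for the accuracy rule or the Section 9.4 exclusions, so neither 200 completers nor 80% two-sided power is secured

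*Combined protocol and SAP*

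**What the plan says.** Section 3.2 sets the numbers: "The study requires up to 400 volunteers (200 completers) successfully complete the study to run statistical analyses". Both the enrolment figure and the attrition figure are ceilings: "We anticipate up to 50% drop-out between study session 1 and 2". The recruitment posting in Appendix A carries the same limit: "Number of assignments per HIT: 400".

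Returning for the second session does not by itself make a volunteer a completer. Section 3.2 defines that status as "completing the HBMT with at least 60% of the stems completed correctly and participating at both T1 and T2".

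Section 7.2 takes d = 0.4 and concludes that "a minimum of 200 completers who follow all task instructions will be needed to achieve 80% power", split as 100 per condition. It does not say whether the test is one- or two-sided.

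Section 9.4 does not impute. It removes volunteers with more than 15% missing data listwise and handles smaller amounts pairwise. On outliers it says "Outliers will be identified as such in the database, and will not be included in data analyses", but the same sentence goes on to allow transformation instead. No section gives an expected rate for accuracy failures, missing data or outliers.

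Section 9.1 names a mixed ANOVA for anger and HAB and a GLM for aggression. Section 9.2 sets alpha at 0.05, with one-tailed tests for the directional hypotheses of Section 5.1 where the test is itself directional.

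**The concern.** The stated attrition covers only loss between the two sessions. It accounts for the whole step from 400 to 200, so nothing is set aside for returners who fail the accuracy rule or for data removed under Section 9.4. The 200 is also described as a minimum, with no spare power behind it if the calculation was two-sided.

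At stake is whether the stated size and power describe what the design gives when attrition reaches the level it was planned for. If they do not, a null result could be read as coming from a study with 80% power when the analysed sample had less.

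**Working it through.** **Inputs.** Enrolment cap 400 (Sections 3.2 and 7.1, Appendix A). Drop-out at most 50% (Section 3.2). d = 0.4, 100 completers per arm and 80% power (Section 7.2). Alpha 0.05 (Section 9.2). The further exclusion rate x among returners is not in the documents; 5-20% is assumed below to show a range.

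**1. Reproduce the 200.** Use a two-sample t test with n per arm, 2n - 2 degrees of freedom and noncentrality d x sqrt(n/2). For n = 100 the noncentrality is 0.4 x sqrt(50) = 2.83.
- Two-sided 0.05: power at 100 per arm is 80.4%, and 100 is the smallest n per arm reaching 80%. This matches the plan.
- One-sided 0.05: power at 100 per arm is 88.0%, and 80% needs only 78 per arm (156 in total). This does not match.

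The plan's figure is therefore a two-sided one, although Section 7.2 does not say so.

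**2. Reproduce the 400.** 200 / (1 - 0.50) = 400. Between-session attrition is the only loss allowed for.

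**3. Margin at the bound.** Returners = 400 x (1 - 0.50) = 200. Completers = 200 minus accuracy failures, so one failure is enough to fall short. On power, 99 per arm gives 79.97% two-sided.

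**4. Effect of further exclusions at the bound.** Analysed number = 200 x (1 - x).

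| Assumed x | Analysed | Per arm | Two-sided power | One-sided power |
|---|---|---|---|---|
| 0% | 200 | 100 | 80.4% | 88.0% |
| 5% | 190 | 95 | 78.3% | 86.5% |
| 10% | 180 | 90 | 76.1% | 84.8% |
| 15% | 170 | 85 | 73.7% | 83.0% |
| 20% | 160 | 80 | 71.0% | 80.9% |

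**5. Slack below the bound.** The tolerable exclusion rate is 1 - 200 / returners.
- 45% drop-out: 220 return, and 1 - 200/220 = 9.1%.
- 40% drop-out: 240 return, and 1 - 200/240 = 16.7%.

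**6. Return rate needed to keep 200 with 400 enrolled.** Rate = 200 / (400 x (1 - x)).
- x = 5%: 200/380 = 52.6%, about 53%.
- x = 20%: 200/320 = 62.5%, about 63%.

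**The case against.** A reader might infer that the design cannot deliver 200 completers or 80% power. The documents do not support that, for these reasons.

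- **The 50% is a ceiling.** Step 5 shows room for exclusions as soon as drop-out is below it. This stands: the shortfall arises at or near the bound and is not certain. However, 50% is the only attrition figure given, and it is the one that links 200 to 400.
- **The exclusion rates are not the plan's.** This stands for the size of the loss. It does not touch the absence of margin, which needs only 400, 50% and the completer definition.
- **The exclusions differ in kind.** Only the accuracy rule changes the completer count. Section 9.4 acts on the analysed set, partly pairwise; its outlier rule concerns individual scores and permits transformation. This stands, so missing-data and outlier losses should not be counted against the 200 completers.
- **One-tailed testing.** Hypothesis 1 is directional, and under Section 9.2 a one-tailed t test would keep 80% power down to 78 per arm, which covers the whole assumed 5-20% range. This stands as a condition. Against it, the ANOVA and GLM group F tests in Section 9.1 are effectively two-sided, and the 200 reproduces only that way.
- **Covariates.** Section 9.1 adjusts the aggression analysis for trait anger, age and gender. If d = 0.4 is unadjusted and the covariates explain 10% of the variance (an assumption), the effective d is 0.4/sqrt(0.90) = 0.42 and 90 per arm gives 80.3%. With 20% explained, 80 per arm gives 80.3%. The plan claims no such gain in Section 7.2, but the unadjusted powers above are not the only possible values.

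**Conclusion.** The point holds in a conditional form. If drop-out reaches the 50% the plan allows for, the 400 cap gives 200 returners, and any accuracy failure leaves fewer than 200 completers. On the two-sided test that reproduces the sample size, power then drops below 80% with the loss of one volunteer per arm. The fall is about 2 percentage points at 5% excluded and about 9 at 20% (80.4% to 78.3% and 71.0%), on assumed exclusion rates, equal arms and no covariate gain.

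The completer shortfall at the bound does not depend on sidedness; the loss of 80% power does. Because Section 7.2 is silent on sidedness and Sections 9.1 and 9.2 point in different directions, the reader cannot tell which power figure applies.

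**What to change.** Amend Section 7.2 in two respects.

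1. State whether the 80% is one- or two-sided, and reconcile that with the F tests in Section 9.1 and the one-tailed rule in Section 9.2.
2. Then do one of the following:
   - Give the power for the analysed number at the 50% bound, with the exclusion rate labelled as an assumption. For example: 400 enrolled, 50% not returning and 5-20% of returners excluded gives 190-160 analysed, with power of 78.3-71.0% two-sided or 86.5-80.9% one-sided.
   - Give the lowest return rate at which 200 remain after exclusions: about 53% if 5% are excluded, about 63% if 20% are.

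The text should keep completers (session attendance and accuracy) separate from the analysed set (after Section 9.4).

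The cost is wording only. The cap can stay at 400 with no extra enrolment; the stated power becomes slightly less favourable.

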Volunteer recruitment and data collection will be done online by ARL AI's and/or staff with assistance from volunteerscience.com (the online experimental platform). Volunteers will be recruited via Amazon Mechanical Turk (MTurk) to the experimental webpage and complete informed consent electronically. A description of this clinical trial will be available on <http://www.clinicaltrials.gov>. Additionally a copy of the informed consent may be posted to a public website no later than 60 days after enrollment is completed.

Time-point 1: Volunteers will be randomly assigned to complete either the real or fake HBMT. Volunteers will also complete a brief vignette reading HAB activity, a brief measure of trait (what is typical for them) aggression, and state (how they have felt recently) anger.

Time-point 2: Volunteers will be asked to return no sooner than 24 hours and no later than 96 hours from when they completed time-point 1 to complete a following up HAB assessment (second vignette interpretation task) and brief surveys asking about aggressive behaviors and state anger during the preceding 24 hour period.

Mechanism for inviting volunteers back to complete time-point 2: The two-time point nature of this study will be explained to volunteers in both the study advertisement and in the ICD.

Additionally, a feature on MTurk will allow the volunteerscience.com to send a daily e-mail to time-one volunteers inviting them back to time-point two. This can be done without MTurk revealing the e-mail addresses of the volunteers. The e-mail will remind volunteers to please return at any point between 24 hours and 96 hours from when they completed the first time-point.

Upon completion of each time-point, the webpage will thank volunteers for their participation. Volunteers will be paid part of the payment at the end of time-point one and the remaining payment after completing time-point two (see section 10.6).

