## 7 STUDY DESIGN

### 7.1 Overview and Duration of Volunteer Participation

In the present study, we propose to examine the effectiveness of HBMT on reducing anger and aggression in up to 400 volunteers (200 completers) divided into two experimental conditions ( $n = 100$  completers in each group). The duration of participation for each volunteer is approximately 60 minutes total across both time-points (see Section 7.8 for procedure breakdown with estimated times).

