## 8.5 Randomization and Volunteer Assignment

Volunteer assignment to each of the two experimental conditions is semi-randomized (i.e. random except that computer ensure equal sample sizes across experimental conditions). The randomized assigning of participants is done by the study web-page/program at volunteerscience.com. The computer program randomly assigned volunteers to one of the two conditions when they begin the study.

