### **9.6 Selection of Volunteers to be Included in Analyses**

See section 9.4 for situations where volunteer data will be excluded listwise versus pairwise.

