#### **10.6 Financial Incentives to Volunteers**

Volunteers will be paid up to \$5 for their participation in this study. All volunteers who complete time-point one of the study will receive \$3 and volunteers will receive an additional \$2 if they complete time-point two of the study. This rate is standard pay for MTurk work (See Hitlin, 2016). Most MTurk tasks pay 10 cents or less and result in less than an equivalent hourly wage of \$5. Volunteers will not be paid for participation in a time point if they do not complete an entire time point (i.e., progress through each activity/survey and reach the end screen; volunteers may skip any question they do not wish to answer on surveys without affecting payment). If a volunteer is terminated from the study as a result of website, server, or study program related failures (e.g., server goes down during study), they may request payment by contacting the PI directly. The PI will ask Volunteerscience.org to verify that the server/website failure had occurred and if so to pay the volunteer. The approval authority of such requests is the PI. Volunteerscience.com will track the performance of each volunteer using their MTurk handle and calculate compensation appropriately without sharing any PII (including MTurk handle) with ARL or WRAIR staff.

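### The 60%-correct completer rule is scored after randomisation on a task whose instructions differ by arm, and the plan neither defines the scoring nor says whether volunteers below it are analysed

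*Combined protocol and SAP*

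**What the plan says.** Section 3.2 asks that up to 400 volunteers (200 completers) "successfully complete the study to run statistical analyses" and defines a completer as someone "completing the HBMT with at least 60% of the stems completed correctly and participating at both T1 and T2". Section 7.2 says that "a minimum of 200 completers who follow all task instructions will be needed to achieve 80% power". Section 7.1 mentions both the 400 and the 200 and can be read either way.

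Section 9.6, on who is analysed, is one sentence: "See section 9.4 for situations where volunteer data will be excluded listwise versus pairwise". Section 9.4 covers missing data (a 15% cut) and outliers. Neither mentions completers or stem accuracy.

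On timing, section 8.5 says: "The computer program randomly assigned volunteers to one of the two conditions when they begin the study". The procedure in 8.8 places the training after that.

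On the task, 8.7.1 and Appendix E tell the real arm to type only non-negative words and to leave negative-only stems blank. The fake arm is told to type any word that completes the stem. Section 3.3(a), however, describes the task for all volunteers as forming non-aggressive words.

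On follow-up, the platform will "send a daily e-mail to time-one volunteers inviting them back to time-point two", with no accuracy condition. Section 10.6 treats a time-point as complete when volunteers "progress through each activity/survey and reach the end screen".

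**The concern.** Randomisation makes the arms comparable at assignment. A filter applied afterwards, on performance in a task that differs by arm, can undo that even if the training does nothing. Section 6.1 says that people who complete ambiguous fragments with hostile words tend to react more aggressively. If the filter penalises hostile words in one arm only, that arm is left with less aggressive people.

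Aggression is the outcome most exposed. It is part of Hypothesis 1, is measured only at time-point two, and so has no baseline value to subtract. Section 9.2 tests it one-tailed. With the scoring and the analysis set both open, either could also be settled after the data are seen.

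**Working it through.** **1. The plan's own figure.** For d = 0.4, alpha 0.05 and 80% power, a two-sided t-test needs about 100 per arm, or 200 in all, as 7.2 states. Power at 100 per arm is 80.4% two-sided and 88.0% one-tailed. Allowing for 50% drop-out, 200/0.5 = 400, as stated. That cap leaves no room for further loss to the 60% rule. If 50% drop out and 10% or 20% of returners fail the rule, 400 × 0.5 × 0.9 = 180 or 400 × 0.5 × 0.8 = 160 completers remain.

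**2. The threshold.** Appendix E lists 80 stems: 20 positive/neutral, 20 negative and 40 ambiguous. Two, two and three of these are marked as practice, leaving 18 + 18 + 37 = 73. Then 0.6 × 73 = 43.8, so 44 are needed.

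**3. What passing takes under each scoring.**

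- *Own instructions, correct blanks credited.* A real-arm volunteer who withholds on all 18 negative stems needs 44 − 18 = 26 of the other 55 (47%), but hostile words on ambiguous stems are errors. A fake-arm volunteer needs any 44 of 73 (60%), and hostile words cost nothing. Example: 13 positive stems filled, 26 ambiguous filled (5 with hostile words), 9 negative filled and 9 left blank. Fake arm: 13 + 26 + 9 = 48/73 = 66%, pass. Real arm: 13 + 21 + 9 = 43/73 = 59%, fail. Selection on hostility falls on the real arm, which tilts towards the training.
- *Own instructions, only typed words credited.* An obedient real-arm volunteer can reach at most 55/73 (75%) and needs 44/55 (80%). The tilt has the same direction, with far more real-arm failures.
- *Non-hostile words required in both arms, as 3.3(a) suggests.* A fake-arm volunteer who fills the negative stems and solves all 18 positive ones still needs 26 of 37 ambiguous stems (70%) non-hostile, without being asked for that. Selection falls mainly on the fake arm, which tilts against the training.
- *Any valid word counts.* There is no tilt by hostility. Pass rates still differ by arm if withheld stems stay in the denominator, and are equal if those stems are removed.

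**4. Size, on assumed inputs.** Suppose a fraction f of one arm is removed at the hostile end, and the screened score correlates ρ with aggression. The false difference is ρ·φ(z_f)/(1 − f), where z_f is the f quantile of the standard normal. For ρ = 0.2 and f = 0.2 this is 0.2 × 0.280/0.8 = 0.07 SD. With standard error √(2/100) = 0.141, the one-sided error when the real arm is selected is Φ(0.07/0.141 − 1.645) = 12.5%. Over ρ = 0.1 to 0.3 and f = 5% to 30%, the difference is 0.01 to 0.15 SD and the error 6% to 28%. This is before covariate adjustment. If the fake arm is selected instead, the sign reverses.

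A null simulation with trait-anger adjustment used 243 combinations: solve rate 65–80%, hostile completions 15–25%, withholding 50–100%, hostility–aggression correlation 0.2–0.4, trait–hostility correlation 0.3–0.5 and trait–aggression correlation 0.4.

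- Own instructions, blanks credited: about 0 to 0.15 SD towards the training, median 0.02, above 0.10 in 3% of combinations. One-tailed error had median 6.5% and maximum 17%. The larger values need about half of withholds to fail. With only 5% or 10% hostile completions in the real arm, the median bias was 0.005 or 0.010 SD.
- Own instructions, typed words only: 0 to 0.30 SD, median 0.11, with 4–32% passing in the real arm against 66–94% in the fake arm.
- Non-hostile words required in both arms: about 0 to 0.11 SD against the training in one run, and 0.02 to 0.17 SD (median 0.06) in another on a different set of assumptions.
- Any valid word: within 0.003 SD of zero. With withheld stems kept in the denominator, 20–84% pass in the real arm against 66–94%.

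State anger is analysed as change from time-point one, so a stable difference in the people kept largely cancels.

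**The case against.** Nothing in section 9 says that completers are the analysis set, so this may be a recruitment target and no more. That is a fair reading of section 9 alone. But 3.2 ties completers to running the analyses, 7.2 powers on them, and no analysis of all returners is stated, so a completer analysis is the natural inference.

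The trait-anger covariate in 9.1 removes part of any bias in aggression, and volunteers told to avoid hostile words may produce few of them. Both points stand, and they are why the likely size is small. The largest figures come from crediting typed words only. That would fail most obedient real-arm volunteers and is unlikely to be intended. The worked answer sheet shows only that the bar differs by arm, because the instructions would themselves change the answers.

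A reader might infer that the rule favours the training. The documents do not support that: 3.2 does not define the scoring, and 3.3(a) supports a reading that works against it. A reader might also infer that everyone below 60% will have time-2 data. Some will, because all are invited back, but 3.2 expects up to half not to return. Finally, Appendix E marks seven practice stems while its instructions say five. That moves the threshold from 44/73 to 45/75 and lends no support to the bias argument.

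**Conclusion.** The concern holds as a gap in the analysis set and the scoring, and should be fixed before data are seen. A completer analysis would not be a comparison of the groups as randomised, and it could shift the aggression result in either direction or in neither. The size is undetermined. On assumed inputs the adjusted bias is usually a few hundredths of an SD, against a planned effect of 0.4, and reaches about 0.1 SD or more only with frequent hostile completions, poor withholding or stronger correlations. The argument also assumes that the link in 6.1 between hostile completions and aggression carries over to this task and to self-reported daily behaviour.

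**What to change.** State in 9.6 that the primary analysis includes every randomised volunteer with time-2 data, in the assigned arm, whatever the stem accuracy. Use the 60% rule only in a sensitivity analysis scored the same way in both arms, for example on the 18 scored positive/neutral-only stems, where both arms are asked to type a word. Define correct completion and its denominator in 3.2, reconcile the five and seven practice trials, and report rule failures by arm.

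The change is wording only, since returners' data are collected anyway. The price is dilution. If 10% or 20% of returners gain nothing, d falls to 0.4 × 0.9 = 0.36 or 0.4 × 0.8 = 0.32, and one-tailed power at 100 per arm is 81% or 73%. Removing exactly those people would give 85% (90 per arm) or 81% (80 per arm) at d = 0.4, but the 60% score is unlikely to identify them exactly. The sensitivity screen is still applied after randomisation, and the change does not address bias from drop-out between the two time-points.
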